3.1.5 Data Review

A review committee will be used to review data as specified in the Pathology Review Charter and Steering Committee Charter. This committee will include Genentech study team members, study investigators, and may also include external consultants, as needed.

3.2 END OF STUDY AND LENGTH OF STUDY

The end of this study is defined as the date when the last data point required for survival follow-up is received from the last patient. This is expected to occur approximately 3 years after the last patient receives the last dose of adjuvant atezolizumab.

The Neoadjuvant Atezolizumab Therapy Phase will end when the last data point required for primary efficacy analysis (i.e., pathology evaluation at time of surgery) is obtained. This is expected to occur approximately 30 days after the last patient's surgery.

The Surveillance period will end 2 years after the Post-surgery Visit.

After completing neoadjuvant or adjuvant treatment with atezolizumab, patients will be followed for survival for up to 3 years. For patients that undergo surgery and enter Surveillance, time in Surveillance will overlap with time in Survival Follow-up (see [Appendix 2](#)).

The total length of the study, from screening of the first patient to the end of the study, is expected to be approximately 6 years.

3.3 RATIONALE FOR STUDY DESIGN

3.3.1 Rationale for Atezolizumab Dose and Schedule

The fixed dose of 1200 mg (equivalent to an average body weight-based dose of 15 mg/kg) was selected on the basis of both nonclinical studies described in [Section 1.2.1](#) and available clinical data from Study PCD4989g as described below.

The target exposure for atezolizumab was projected on the basis of nonclinical tissue distribution data in tumor-bearing mice, target-receptor occupancy in the tumor, the observed atezolizumab interim pharmacokinetics in humans, and other factors. The target trough concentration (C_{trough}) was projected to be 6 μ g/mL on the basis of several assumptions, including the following: 1) 95% tumor-receptor saturation is needed for efficacy and 2) the tumor-interstitial concentration to plasma ratio is 0.30 based on tissue distribution data in tumor-bearing mice.

The atezolizumab dose is also informed by available clinical activity, safety, pharmacokinetics, and immunogenicity data. Anti-tumor activity has been observed across doses from 1 mg/kg to 20 mg/kg q21d. The MTD of atezolizumab was not reached, and no DLTs have been observed at any dose in Study PCD4989g. Currently available PK and ATA data suggest that the 15-mg/kg atezolizumab q3w regimen (or fixed-dose equivalent) for Phase II and Phase III studies would be sufficient to both maintain $C_{trough} \geq 6 \mu$ g/mL and further safeguard against both interpatient variability and the potential effect of ATAs that could lead to subtherapeutic levels of atezolizumab relative to the 10-mg/kg atezolizumab q3w regimen (or fixed-dose equivalent). From inspection of available observed C_{trough} data, moving further to the 20-mg/kg

atezolizumab q3w regimen does not appear to be warranted to maintain targeted C_{trough} levels relative to the proposed 15-mg/kg atezolizumab q3w level.

Simulations (Bai et al. 2012) do not suggest any clinically meaningful differences in exposure following a fixed dose or a dose adjusted for weight. Therefore, a fixed dose of 1200 mg has been selected (equivalent to an average body weight-based dose of 15 mg/kg). Selection of an every-21-day dosing interval is supported by this preliminary PK evaluation.

Refer to the Atezolizumab Investigator's Brochure for details regarding nonclinical and clinical pharmacology of atezolizumab.

3.3.2 Rationale for Patient Population

While the addition of adjuvant cisplatin based chemotherapy following surgical resection of early stage NSCLC has produced significant survival benefits (Pignon et al. 2008), rates of local and distant disease relapse leading to death remain unacceptably high. Studies show that neoadjuvant chemotherapy has approximately the same benefit as adjuvant (Felip et al. 2010). Recently, immunotherapy with antibodies that bind to checkpoint inhibitors such as PD-1 and PD-L1 have been shown to produce long lasting responses in some patients with advanced NSCLC who were refractory to standard chemotherapy (Brahmer et al. 2015). Therefore this study population was chosen to primarily determine the ability of atezolizumab to produce objective responses in patients undergoing curative intent surgery for Stage IB-IIIA NSCLC. This study will also explore impact of adjuvant atezolizumab on long term survival outcomes.

3.3.3 Rationale for Biomarker Assessments

It is currently thought atezolizumab functions through preventing suppression of CD8 cytotoxic T-cell function, but the details of this process as well as the impact of atezolizumab on additional immune cell populations is thus far undefined. Cancer can escape the immune system through multiple mechanisms including the manipulation of cells with immunosuppressive phenotypes. In addition, it has been shown that elements of both the innate and adaptive immune systems have anti-tumor functions. As a result, it is necessary to study the global immune modulatory effects of atezolizumab to further elucidate its mechanism of action in different patients with lung cancer.

Furthermore, it has been hypothesized that atezolizumab efficacy shown in smoking-associated lung cancer and melanoma is due to the high mutational burden of these diseases, leading to the generation of immune stimulating neoantigens. Recently, it has been shown that somatic mutations present within tumor cells are capable of eliciting tumor specific T-cell responses (Tran et al. 2014). The identification of somatic mutations in NSCLC producing immune stimulating mutant peptides may help to better select patients for treatment with atezolizumab and provide information about potential vaccine immunotherapy approaches. As mentioned previously, the number of mutations determined by WES has been shown to perform as another predictive biomarker (Rizvi

et al. 2015). Therefore, WES will be performed with comparison to control normal DNA to enable direct determination of mutational load and the spectrum of mutations present using tumor tissue and/or blood. In addition, atezolizumab is proposed to reverse exhaustive status of T-cell responses against cancer that was associated with PD-1 expression (Barber et al. 2006; Dong et al. 2002). The impact of such mutations on treatment with atezolizumab and similar agents is unknown, and their identification could help identify patients for treatment.

Tumor tissue samples will be obtained pre-treatment, at resection and at disease progression/recurrence (if available) for, including, but not limited to immunohistochemistry, immunofluorescence microscopy, next generation sequencing (e.g. RNA sequencing, whole exome sequencing, TCR sequencing). Furthermore, digital pathology and machine-learning approaches may be applied in this study to derive predictive histological signatures or to explore the applicability for digital assessment of major pathological response. Adjacent normal lung tissue may be obtained at resection to allow comparisons with the tumor immune microenvironment.

Whole blood and lymph nodes will be obtained to analyze, including but not limited to, changes in the phenotype and function of immune cell subtypes by flow cytometry and may be used, but not limited to assess T-cell receptor clonality by NGS, gene expression profiling and monitoring of anti-tumor immunity using functional assays.

After surgical resection, routine clinical surveillance involves repeated radiographic imaging and monitoring of clinical symptoms for disease recurrence. Blood-based biomarkers can help to better understand disease recurrence and improve the development of future adjuvant treatment options (Chaudhuri et al. 2017). Blood samples obtained during Surveillance will be used for serial ctDNA analysis by NGS and may include, but is not limited to, immune profiling by NGS or flow cytometry and functional T-cell assays.

Patients whose disease progresses or recurs anytime between the neoadjuvant phase and end of Surveillance will be asked to consent to an optional tissue biopsy (tumor and lymph node, if available) at the time of progression or recurrence. The biopsy may be used to explore if radiographic findings are consistent with histological presence of tumor and/or if the appearance of recurrence was caused by tumor immune infiltration. In addition, the tissue may be used for biomarker research to explore mechanisms of resistance and recurrence to therapy. This exploratory biomarker analysis will not be used for any treatment-related decisions.

See Section 2 for details for secondary and exploratory laboratory analyses.

4. **MATERIALS AND METHODS**

4.1 **PATIENTS**

Approximately 180 patients with histologically documented Stage IB, II, IIIA, and selected IIIB NSCLC and are eligible for surgical resection with curative intent will be enrolled in the Neoadjuvant Atezolizumab Therapy Phase of this study. Approximately 50 patients who complete neoadjuvant atezolizumab therapy are expected to continue on to the Adjuvant Atezolizumab Therapy Phase.

4.1.1 **Inclusion Criteria**

Neoadjuvant Atezolizumab Therapy

Patients must meet the following criteria for study entry:

- Signed Informed Consent Form
- Age \geq 18 years
- Able to comply with the study protocol, in the investigator's judgment
- Pathologically documented NSCLC
 - Stage IB, II, IIIA, or selected IIIB, including T3N2 or T4 (by size criteria, not by mediastinal invasion) NSCLC (based on the 8th edition of the American Joint Committee on Cancer [AJCC] Non-Small Cell Lung Cancer Staging system; see [Appendix 4](#)). Note: Patients may be enrolled based on clinical stage, but documentation of nodal involvement by endobronchial ultrasound (EBUS) or mediastinoscopy for patients with clinical Stage II and IIIA disease is encouraged.
- Measurable disease, as defined by RECIST v1.1
- NSCLC must have a solid or subsolid appearance on CT scan and cannot have a purely ground glass opacity (GGO) appearance. For subsolid lesions, the tumor size (i.e., clinical T stage) should be measured based on the solid component only, exclusive of the GGO component
- Evaluated by the operating attending surgeon prior to study enrollment to verify that the primary tumor and any involved lymph nodes are technically completely resectable
- Adequate pulmonary function to be eligible for surgical resection with curative intent
 - Pulmonary function tests (PFTs) must have been performed within 6 months of planned resection and repeated at screening and should include lung volumes, spirometry, and a diffusion capacity. Abnormal PFTs may be further evaluated with quantitative ventilation/perfusion scanning or cardiopulmonary exercise testing. Postoperative percent predicted forced expiratory volume in 1 second (FEV1) and diffusion capacity must be $\geq 40\%$ and/or maximal oxygen consumption (VO_2 max) should be > 10 mL/kg/min.

- Adequate cardiac function to be eligible for surgical resection with curative intent
 - If clinically indicated, patients with underlying ischemic or valvular heart disease should be evaluated preoperatively by a cardiologist.
- Availability of at least 2 cores of a pre-treatment formalin-fixed, paraffin-embedded (FFPE) biopsy and at least 1 core of fresh frozen biopsy of the primary tumor (archival sample) or willing to undergo an additional core needle biopsy (CNB; preferred method), EBUS, or bronchoscopy (acceptable alternatives) to provide newly collected samples.
 - For core biopsies, needle sizes of 16–18 gauge are preferred. If a 19 gauge or smaller needle is used, consider adding another pass. In addition, to ensure a quality tissue sample, a rapid on site evaluation (ROSE) methodology is highly recommended to evaluate the adequacy of the sample.
 - If sample is collected during EBUS, at least 3 passes are requested (19–22 gauge needle can be used)
- ECOG Performance Status of 0 or 1 (see [Appendix 7](#))
- Adequate hematologic and end-organ function, defined by the following laboratory results obtained within 14 days prior to the first dose of atezolizumab:
 - ANC $\geq 1500/\mu\text{L}$
 - Platelet count $\geq 100,000/\mu\text{L}$
 - Hemoglobin $\geq 9.0 \text{ g/dL}$; patients may be transfused to meet this criterion.
 - AST and ALT $\leq 2.5 \times$ upper limit of normal (ULN)
 - Serum bilirubin $\leq 1.5 \times$ ULN
 - Serum creatinine $< 3.0 \text{ mg/dL}$
- For women of childbearing potential: agreement to remain abstinent (refrain from heterosexual intercourse) or use a contraceptive method with a failure rate of $< 1\%$ per year during the treatment period and for at least 5 months after the last dose of atezolizumab. Women must refrain from donating eggs during this same period.
 - A woman is considered to be of childbearing potential if she is postmenarcheal, has not reached a postmenopausal state (≥ 12 continuous months of amenorrhea with no identified cause other than menopause), and has not undergone surgical sterilization (removal of ovaries and/or uterus).
- Examples of contraceptive methods with a failure rate of $< 1\%$ per year include bilateral tubal ligation, male sterilization, hormonal contraceptives that inhibit ovulation, hormone-releasing intrauterine devices, and copper intrauterine devices.
- The reliability of sexual abstinence should be evaluated in relation to the duration of the clinical trial and the preferred and usual lifestyle of the patient. Periodic abstinence (e.g., calendar, ovulation, symptothermal, or postovulation methods) and withdrawal are not acceptable methods of contraception.

Adjuvant Atezolizumab Therapy Phase

Patients must meet the following criteria to be eligible to continue to receive atezolizumab adjuvant therapy:

- ECOG Performance Status of 0 or 1 (see [Appendix 7](#))
- Adequate hematologic and end-organ function, defined by the following laboratory results obtained per SOC prior to the starting adjuvant atezolizumab in the Adjuvant Atezolizumab Therapy Phase:
 - ANC $\geq 1500/\mu\text{L}$
 - Platelet count $\geq 100,000/\mu\text{L}$
 - Hemoglobin $\geq 9.0 \text{ g/dL}$; patients may be transfused to meet this criterion
 - AST and ALT $\leq 2.5 \times \text{ULN}$
 - Serum bilirubin $\leq 1.5 \times \text{ULN}$
 - Serum creatinine $< 3.0 \text{ mg/dL}$

4.1.2 Exclusion Criteria

Neoadjuvant Atezolizumab Therapy Phase

Patients who meet any of the following criteria will be excluded from study entry:

- NSCLC that is clinically T4 by virtue of mediastinal organ invasion or Stage IIIB by virtue of N3 disease
- Any prior therapy for lung cancer, including chemotherapy, hormonal therapy, or radiotherapy, within 3 years
- Patients with prior lung cancer that have been in remission for < 3 years
- Prior treatment with anti-PD-1 or anti-PD-L1 therapies or pathway-targeting agents
- Patients with prior allogeneic bone marrow transplantation or prior solid organ transplantation
- Major surgical procedure within 28 days prior to Cycle 1, Day 1
- Malignancies other than the disease under study within 3 years prior to Cycle 1, Day 1, with the exception of patients with a negligible risk of metastasis or death and with expected curative outcome (such as adequately treated carcinoma in situ of the cervix, basal or squamous cell skin cancer, localized prostate cancer treated surgically with curative intent, or ductal carcinoma in situ treated surgically with curative intent) or undergoing active surveillance per SOC management (e.g., Rai Stage 0 chronic lymphocytic leukemia, prostate cancer with Gleason score ≤ 6 , and prostate-specific antigen (PSA $\leq 10 \text{ ng/mL}$, etc.)
- Treatment with systemic immunosuppressive medications (e.g., prednisone, cyclophosphamide, azathioprine, methotrexate, thalidomide, and anti-tumor necrosis factor [anti-TNF] agents) within 2 weeks prior to Cycle 1, Day 1
 - Patients who have received acute, low-dose, systemic immunosuppressant medications (e.g., a one-time dose of dexamethasone for nausea or premedication for contrast dye allergy) are eligible.

- The use of inhaled corticosteroids for chronic obstructive pulmonary disease (COPD) and mineralocorticoids (e.g., fludrocortisone) for patients with orthostatic hypotension or adrenocortical insufficiency is allowed.
- History or risk of autoimmune disease, including but not limited to systemic lupus erythematosus, rheumatoid arthritis, inflammatory bowel disease, vascular thrombosis associated with antiphospholipid syndrome, Wegener's granulomatosis, Sjögren's syndrome, Bell's palsy, Guillain-Barré syndrome, multiple sclerosis, autoimmune thyroid disease, vasculitis, or glomerulonephritis
 - Patients with a history of autoimmune hypothyroidism on a stable dose of thyroid replacement hormone are eligible.
 - Patients with controlled type 1 diabetes mellitus on a stable insulin regimen are eligible.
 - Patients with eczema, psoriasis, or lichen simplex chronicus or vitiligo with dermatologic manifestations only (e.g., patients with psoriatic arthritis are excluded) are eligible provided they meet the following conditions:
 - Rash must cover < 10% of body surface area (BSA)
 - Disease is well controlled at baseline and only requiring low potency topical steroids (e.g., hydrocortisone 2.5%, hydrocortisone butyrate 0.1%, fluocinolone 0.01%, desonide 0.05%, alclometasone dipropionate 0.05%)
 - No acute exacerbations of underlying condition within the last 12 months (requiring psoralen plus ultraviolet A radiation, methotrexate, retinoids, biologic agents, oral calcineurin inhibitors, high potency or oral steroids)
- History of idiopathic pulmonary fibrosis, pneumonitis (including drug induced), organizing pneumonia (i.e., bronchiolitis obliterans, cryptogenic organizing pneumonia, etc.), or evidence of active pneumonitis on screening chest CT scan
- Known clinically significant liver disease, including active viral, alcoholic, or other hepatitis, cirrhosis, fatty liver, and inherited liver disease
- History of HIV infection
- Active hepatitis B (chronic or acute) defined as having a positive hepatitis B surface antigen (HBsAg) test at screening
 - Patients with past or resolved hepatitis B infection (defined as having a negative HBsAg test and a positive total hepatitis B core antibody (HBcAb) test) are eligible.
- Active hepatitis C virus (HCV) infection, defined as having a positive HCV antibody test and a positive HCV RNA test at screening
- Active tuberculosis

- Administration of a live, attenuated influenza vaccine (e.g., FluMist®) within 4 weeks before Cycle 1, Day 1 or at any time during the study
 - Influenza vaccination should be given during influenza season only (approximately October to March).
- Severe infections within 4 weeks prior to Cycle 1, Day 1, including but not limited to hospitalization for complications of infection, bacteremia, or severe pneumonia
- Received oral or IV antibiotics within 2 weeks prior to Cycle 1, Day 1
 - Patients receiving prophylactic antibiotics (e.g., for prevention of a urinary tract infection or COPD) are eligible.
- Treatment with an investigational agent for any condition within 4 weeks prior to Cycle 1, Day 1 (or within five half-lives of the investigational product, whichever is longer)
- History of severe allergic, anaphylactic, or other hypersensitivity reactions to chimeric or humanized antibodies or fusion proteins
- Pregnant or lactating, or intending to become pregnant during the study
 - Women of childbearing potential must have a negative serum pregnancy test result within 7 days prior to initiation of atezolizumab

Adjuvant Atezolizumab Therapy Phase

- Progressive or recurrent disease as documented by CT scan (per RECIST v1.1 criteria) at the end of SOC adjuvant therapy
 - Patients with radiographic progression/recurrence and no evidence of pathologic response of the study during the Neoadjuvant Phase are not eligible for the Adjuvant Atezolizumab Therapy Phase

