4.5.8 Laboratory, Biomarker, and Other Biological Samples

Samples for the following tests will be sent to the study site's local laboratory for analysis:

- Hematology: CBC, including WBC count, RBC count, hemoglobin, hematocrit, platelet count, differential count (neutrophils, eosinophils, basophils, monocytes, lymphocytes, other cells)
- Chemistry panel (serum): sodium, potassium, chloride, bicarbonate, glucose, BUN or urea, creatinine, total protein, albumin, phosphorus, calcium, total and direct bilirubin, alkaline phosphatase, ALT, AST, uric acid, LDH
- Coagulation: international normalized ratio (INR), activated partial thromboplastin time (aPTT), prothrombin time (PT)
- Viral serology: HIV, HBsAg, antibodies against HBsAg, hepatitis B core antigen, and HCV antibody (anti-HCV)
 - HBV DNA is required if a patient has a positive anti-HBc antibody test.
- Pregnancy test: All women of childbearing potential will have a serum pregnancy test at screening.
- Urinalysis, including dipstick (pH, specific gravity, glucose, protein, ketones, blood)
- Thyroid function testing (TSH, free T3, free T4)
- C-reactive protein (CRP)

Samples listed below for biomarker analyses will be sent to one or several central laboratories for storage and/or analysis (see [Table 4](#)). Analyses may include, but are not limited to the analysis of DNA, RNA, and proteins using immunohistochemistry, next generation sequencing, functional T-cell assays, and flow cytometry. Additional assays

may be performed as technology and science are rapidly evolving. For sampling procedures, sample processing, storage conditions, and shipment instructions, refer to the laboratory manual.

- Archival or newly collected sample (fresh frozen tumor tissue and FFPE sample) for secondary and exploratory biomarker objectives.
 - If archival FFPE and fresh frozen tissue are not available, a new pre-treatment CNB (preferred), EBUS, or bronchoscopy (acceptable alternatives) will be required. The new samples will be obtained solely for the purpose of research studies (pre-treatment sample). The number of cores obtained will be determined by the radiologist performing the procedure, based on the patient's clinical condition at the time of biopsy, but will ideally include 5 core biopsies (minimum of 3 [2 FFPE, and 1 fresh frozen]). The additional 2 fresh frozen cores are optional.

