(Window [Days])	Day –42 to –1	Day –14 to –1	C1D1 (Day 1 ± 3) ⁱ	C2D1 (Day 22 ± 3) ⁱ	Day 36 (± 3)	Day 40 (± 10) ^j	4–6 weeks after surgery	30 (± 5) days after last dose	Every 6 weeks to 3 months for up to 2 years ^k	Adjuvant Cycle 1, Day 1, (± 5) days	Adjuvant Cycle 2–17, Day 1 (± 5) days ⁱ	30 (± 5) days after last dose	30 days after progression/ recurrence (± 5) days ^l	Up to 3 years
Informed consent (prescreening ICF and main ICF) ^m	x													
Prescreening biopsy	See footnote ⁿ													
Medical history and demographic data ^o	x													
Weight	x									x	x			
Height	x													
Complete physical examination ^p	x				x ^q									
Limited physical examination ^r					x		x			x	x ^s	x		

Appendix 1
Schedule of Activities (cont.)

Assessment	Screening ^a	Part 1 – Atezolizumab Neoadjuvant Treatment	Surgery			Neo- adjuvant Atezo Treatment Completion/ D/C ^d , See Appendix 2	Surveillance			Disease Progression or Recurrence ^g	Survival Follow- up ^h			
			Pre- surgery ^b	Surgery	Post- Surgery/ Surveillance Baseline ^c		All Subgroups	For Subgroups B and D only						
							Surveillance for All Treatment Subgroups	Adjuvant Atezo Treatment ^{e,f}	Adjuvant Atezo Treatment ^{c,f}	Adjuvant Atezo Treatment Completion ^{/D/C ^d}				
(Window [Days])	Day –42 to –1	Day –14 to –1	C1D1 (Day 1 ± 3)	C2D1 (Day 22 ± 3) ⁱ	Day 36 (± 3)	Day 40 (± 10) ^j	4–6 weeks after surgery	30 (± 5) days after last dose	Every 6 weeks to 3 months for up to 2 years ^k	Adjuvant Cycle 1, Day 1, (± 5) days	Adjuvant Cycle 2–17, Day 1 (± 5) days ⁱ	30 (± 5) days after last dose	30 days after progression/ recurrence (± 5) days ^l	Up to 3 years
ECOG Performance Status ^t	x						x		x ^t	x ^t	x			
Vital signs ^u	x		x ^u	x		x		x	x ^u	x ^u	x			
Tumor and response evaluations ^v	x			x		x ^{w, x}		x ^w	x ^{y, x}	x				
Pathologic response assessment ^z						x								
Pulmonary function tests	x ^{aa}			x										
Hematology ^{bb}		x		x	x				x					
Chemistry ^{cc}		x		x	x				x					
Coagulation (aPTT and INR)		x												
Pregnancy test ^{dd}		x												

Appendix 1
Schedule of Activities (cont.)

Assessment	Screening ^a	Part 1 – Atezolizumab Neoadjuvant Treatment	Surgery			Neo- adjuvant Atezo Treatment Completion/ D/C ^d See Appendix 2	Surveillance				Disease Progression or Recurrence ^g	Survival Follow- up ^h		
			Pre- surgery ^b	Surgery	Post- Surgery/ Surveillance Baseline ^c		All Subgroups	For Subgroups B and D only						

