Notes: All assessments should be performed within the time windows specified for the scheduled visit. All designated procedures are required at each visit, even if visit is outside the recommended time window. On treatment days, all assessments should be performed prior to dosing, unless otherwise specified.

- ^a Results of SOC assessments performed prior to obtaining informed consent and within 42 days prior to Day 1 (or within 14 days prior to Day 1 for laboratory tests) may be used; such assessments do not need to be repeated for screening.
- ^b Preferably, assessments at this visit should be performed by the surgeon, if feasible. If not feasible, the assessments may be performed by the Medical Oncologist.
- ^c It is acceptable for visit to occur outside the recommended window; all indicated procedures should be still be performed.

Appendix 1

Schedule of Activities (cont.)

- ^d For the Adjuvant Atezolizumab Therapy Phase, all vital sign measurements and routine laboratory tests and tumor assessments, will be performed per SOC except biomarkers assessments and Extended Chest CT scan, which will occur per Surveillance schedule of activities ([Appendix 2](#)).
- ^e Patients who prematurely discontinue neoadjuvant atezolizumab will return to the clinic 30 (+5) days after the last dose of atezolizumab treatment. If patients undergo surgery after neoadjuvant atezolizumab discontinuation/completion and will not receive adjuvant atezolizumab, the Treatment Discontinuation Visit assessments can be performed at the Post-Surgery Visit (even if it is more than 30 days after the last dose). If the patient will receive adjuvant atezolizumab, the Treatment Discontinuation Visit will occur when the patient completes/discontinues adjuvant atezolizumab treatment. Patients who do not complete surgery will then be followed for survival. Patients who complete surgery will enter the Surveillance period. The visit at which progressive disease or recurrence occurs may be used as the Treatment Discontinuation Visit.
- ^f Any assessments not marked with an "x" should be performed as per SOC.
- ^g Disease progression/recurrence must be confirmed by tumor imaging.

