- ^y For Group D only: Extended CT chest (including liver and adrenals) needs to be done after completion of SOC adjuvant Chemotherapy/Radiotherapy and before initiation of adjuvant atezolizumab to rule out disease progression/recurrence. If done as part of a surveillance visit, it does not need to be repeated. The other tumor assessments will sync with the surveillance visits (see [Appendix 2](#)).
- ^z For the Neoadjuvant Atezolizumab Therapy Phase, pathologic responses will be scored by a pathologist based on the surgical resection as defined by (Hellmann et al. 2014).
- ^{aa} Can be performed within 6 months of planned resection and repeated at screening.
- ^{bb} Hematology includes CBC (WBC count, RBC count, hemoglobin, hematocrit, platelet count, differential count [neutrophils, eosinophils, basophils, monocytes, lymphocytes, other cells]).
- ^{cc} Chemistry panel (serum) includes sodium, potassium, chloride, bicarbonate, glucose, BUN or urea, creatinine, total protein, albumin, phosphorus, calcium, total and direct bilirubin, alkaline phosphatase, ALT, AST, uric acid, LDH.
- ^{dd} All women of childbearing potential, including those who have had a tubal ligation, will have a serum pregnancy test at screening.
- ^{ee} Includes specific gravity, pH, glucose, protein, ketones, and blood.
- ^{ff} Perform thyroid function tests at baseline, the pre-surgery visit, at post-surgery visit and then approximately every 9 weeks (3 cycles) during adjuvant atezolizumab treatment in the Adjuvant Atezolizumab Therapy Phase.
- ^{gg} Viral serology includes HIV, Hepatitis B (HBsAg, antibodies against HBsAg, hepatitis B core antigen; HBV DNA is required positive anti-HBc antibody test), and HCV antibody (anti-HCV).

Appendix 1

Schedule of Activities (cont.)

hh See [Appendix 3](#) for detailed schedule.

ii Tumor tissue may be archival; it does not need to be collected within 42 days of enrollment.

jj Tissue biopsy (tumor and lymph node, if available); at disease progression/recurrence is optional and requires a separate ICF signature. Tissue collection by CNB is preferred, however collection by EBUS, or bronchoscopy are acceptable alternatives.

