	Surveillanc e for All Treatment Subgroups See Appendix 2	Adjuvant Atezo Treatment e,f	Adjuvant Atezo Treatment c,f	Adjuvant Atezo Treatment Completion /D/C d										
(Window [Days])	Day -42 to -1	Day -14 to -1	C1D1 (Day 1±3) i	C2D1 (Day 22 ±3) i	Day 36 (±3)	Day 40 (±10) j	4–6 weeks after surgery	30 (± 5) days after last dose	Every 6 weeks to 3 months for up to 2 years k	Adjuvant Cycle 1, Day 1, (±5) days	Adjuvant Cycle 2–17, Day 1 (±5) days l	30 (± 5) days after last dose	30 days after progressio n/ recurrence (± 5) days l	Up to 3 years
Optional bronchial brushing mm	x									x oo				
Atezolizumab administration pp			x	x						x	x			
Concomitant medications qq	x	x	x	x	x	x	x			x	x			
Adverse events rr	x	x	x	x	x	x	x			x	x			
Survival and recurrence follow-up h													x	

atezo = atezolizumab; C1D1 = Cycle 1, Day 1; C2D1 = Cycle 2, Day 1; D/C = discontinuation; ECG = electrocardiogram; ECOG = Eastern Cooperative Oncology Group; eCRF = electronic Case Report Form; q = every; SOC = standard of care.

Notes: All assessments should be performed within the time windows specified for the scheduled visit. All designated procedures are required

---

at each visit, even if visit is outside the recommended time window. On treatment days, all assessments should be performed prior to dosing, unless otherwise specified.

- a Results of SOC tests or examinations performed prior to obtaining informed consent and within 42 days prior to Day 1 (or within 14 days prior to Day 1 for laboratory tests) may be used; such tests do not need to be repeated for screening.
- b Preferably, assessments at this visit should be performed by the surgeon, if feasible. If not feasible, the assessments may be performed by the Medical Oncologist.
- c It is acceptable for visit to occur outside the recommended window; all indicated procedures should be still be performed.
- d For the Adjuvant Atezolizumab Therapy Phase, all vital sign measurements and routine laboratory tests and tumor assessments, will be performed per SOC except biomarkers assessments and Extended Chest CT scan, which will occur per Surveillance schedule of activities ([Appendix 2](#)).

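### The 7-day pregnancy-test criterion is not assured by the schedules, which place the only test in a 14-day window and allow older routine results to stand without repeat

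*Protocol*

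**What the plan says.** Under the neoadjuvant heading of Protocol Section 4.1.2, pregnancy is an exclusion, with the condition that "Women of childbearing potential must have a negative serum pregnancy test result within 7 days prior to initiation of atezolizumab". The synopsis repeats the same 7-day limit.

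The operational text is looser:

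- **Protocol Appendix 1, pregnancy-test row:** one mark, in the Day -14 to -1 screening column, and none in any later column.
- **Protocol Appendix 1, footnote a:** standard-of-care assessments done before consent count if they meet a 42-day limit, with a shorter limit for laboratory work: "or within 14 days prior to Day 1 for laboratory tests) may be used; such assessments do not need to be repeated for screening".
- **Protocol Appendix 1, footnote dd:** "All women of childbearing potential, including those who have had a tubal ligation, will have a serum pregnancy test at screening".
- **Protocol Section 4.5.8:** "Pregnancy test: All women of childbearing potential will have a serum pregnancy test at screening".
- **SAP Section 4:** the same row with the same single mark, and the same re-use rule in its footnote a: "within 14 days prior to Day 1 for laboratory tests) may be used; such tests do not need to be repeated for screening".

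None of these five places mentions 7 days or exempts the pregnancy test from the 14-day allowance.

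**The concern.** The criterion and the schedule give different maximum ages for the same result. Study staff commonly work from the schedule and its footnotes. A coordinator who draws the test on Day -10, or accepts a routine result from that day, has completed every scheduled item, and nothing in the schedule prompts a repeat before the first infusion. The patient would then be dosed without the evidence that Section 4.1.2 requires.

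Two things are at stake. One is patient safety, because the criterion exists to avoid exposure in early pregnancy. The other is compliance, because such a patient is an eligibility deviation, and Protocol Section 9.2 does not allow eligibility criteria to be waived in advance. The analysis is not at stake. No population in SAP Section 5 depends on the pregnancy test, and neither the sample size nor the primary test is touched.

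**Working it through.** The plan gives no figure to reproduce. The check is a comparison of windows and a count of days.

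**Inputs**

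- Maximum age under the criterion: 7 days before first dose (Protocol synopsis and Section 4.1.2).
- Scheduled window: Day -14 to Day -1, which is 14 calendar days (Protocol Appendix 1; SAP Section 4).
- Re-use limit: 14 days before Day 1 for laboratory tests (footnote a in both schedules).
- First-dose visit: Day 1 ± 3 days (Protocol Appendix 1).
- Convention assumed: there is no Day 0, so Day -1 is one day before Day 1. The screening column is taken as anchored to the nominal Day 1.

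**Age of the oldest test that the schedule allows**

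- Dosing on Day 1: Day -14 to Day 1 is 14 days, and 14 / 7 = 2 times the criterion.
- Dosing at the late limit, Day 4: 14 + 3 = 17 days.
- Dosing 3 days early: 14 − 3 = 11 days, still over 7.

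**Share of the scheduled window that meets the criterion**

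- Dosing on Day 1: Day -7 to -1 qualify, which is 7 of 14 days.
- Dosing on Day 4: a Day -4 test is 4 + 3 = 7 days old and a Day -5 test is 8 days old. Only Day -4 to -1 qualify, which is 4 of 14 days.

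**Can the texts be satisfied together?** Yes. The 7-day window lies inside the 14-day column, and a test at screening can also be a test within 7 days. The schedule is therefore wider than the criterion, and compliance with the schedule alone does not establish compliance with the criterion.

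**Does the gap depend on footnote a?** No. Footnote a reaches only standard-of-care results from before consent. A study test drawn after consent on Day -14 to -8 fits the column without it. Footnote a adds that an older routine result need not be repeated for screening.

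**Is the 14-day column right for other tests?** Section 4.1.1 sets a 14-day limit for the hematology and organ-function results, so the column agrees with that criterion. Of the two, only the pregnancy criterion is narrower than the column.

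**The case against.** The strongest reply is that the specific criterion governs. Section 4.5.1 requires screening results to be reviewed against all eligibility criteria before enrollment. Section 4.2 places registration after eligibility has been confirmed, and Section 9.2 bars waivers. On this view a site that doses on a Day -10 test has not followed the protocol, whatever the schedule shows. Footnote a is also limited to routine results from before consent, and it speaks of completing screening, not of meeting a criterion.

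All of this stands. A reader might infer that the safeguard is cancelled, or that the two rules cannot both be met. The documents do not support that reading, because the 7-day criterion stays in force and a suitably timed test satisfies every passage. The reply does not show that the schedule leads sites to such a test, and no cross-reference tells them that this row has a tighter limit than its column.

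A second tempting reading is that the same rule is broken when treatment resumes after surgery. It is true that no test is marked before adjuvant dosing. The criteria introduced by "Patients must meet the following criteria to be eligible to continue to receive atezolizumab adjuvant therapy" cover performance status and hematologic and organ function, and the adjuvant exclusions cover progression or recurrence. But the 7-day criterion sits under the neoadjuvant heading, and footnote f to Appendix 1 leaves unmarked assessments to standard of care. This is an omission and contradicts nothing. The contraception requirement in Section 4.1.1 and the duty to report pregnancy in Section 5.4.3.1 also continue to apply.

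**Conclusion.** The mismatch at first dose is real and should be corrected. The criterion allows a result up to 7 days old. The schedules allow one up to 14 days old with dosing on Day 1, or 17 days old at the late limit of the visit window. Between 7 of 14 and 4 of 14 scheduled days meet the criterion for dosing on Day 1 and Day 4 respectively. These counts assume no Day 0 and a screening column fixed to the nominal Day 1.

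The 7-day requirement is binding but not assured by the schedule, which is less than saying that it is not delivered. How many patients could be affected cannot be stated, because the documents give no expected number of women of childbearing potential.

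The adjuvant phase is a secondary note only. Section 4.6.2 makes pregnancy a mandatory reason to stop neoadjuvant or adjuvant atezolizumab, so the sponsor may wish to clarify what standard of care is meant to cover before dosing restarts. The documents do not conflict there.

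**What to change.** Reconcile the following to a single window: the synopsis and Protocol Section 4.1.2; Section 4.5.8; the pregnancy-test row and footnotes a and dd of Appendix 1; and the matching row and footnote a in SAP Section 4. Make footnote a consistent with whichever window the sponsor keeps. If that window is shorter than 14 days, the footnote needs an explicit exception for the pregnancy test, and the row needs a note giving its own limit. The window should be tied to the actual first dose, so that the ± 3-day visit allowance cannot stretch it. Which window applies is the sponsor's decision.

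Optionally, add a sentence to the adjuvant criteria saying whether pregnancy status before adjuvant dosing is left to standard of care, so that they read consistently with Section 4.6.2.

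The cost is an edit to protocol wording and a matching edit to the SAP schedule. In practice it means at most a repeat serum test for women whose screening result falls outside the window kept. No analysis, population or sample-size text changes.
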